This trial is registered on *ClinicalTrials.gov* (Identifier#: NCT03141281). The trial is a single-site randomized controlled trial (RCT), conducted at Florida State University (FSU; Tallahassee, FL), one of four funded sites of the National Institute of Aging Center for Research and Education on Aging and Technology Enhancement (CREATE). Following a telephone screening and baseline assessments, eligible participants were randomized into one of four conditions: (1) Posit Science's BrainHQ; (2) Rise of Nations, a PC-based video game; (3) Instrumental Activities of Daily Living (IADL) training, on both AARP's Driver Safety Course, and a Financial Fraud training course developed for this intervention; (4) active control group, playing a suite of three tasks (i.e., Sudoku, crossword puzzles, and word search). Once participants were assigned to a condition, they received a laptop with specialized software for their condition. Participants received in-lab training designed to encourage familiarity with how to operate a laptop, and the necessary components for their task. Participants were asked to train on their assigned condition for four weeks at home, and return for two scheduled days of post-training assessments, as well as a follow-up assessment at 12 months. The overall study design and contact schedule is summarized in Figure 1. The trial had highly standardized protocols for recruitment, screening, assessment, intervention administration (including manuals sent home with participants), and data transfer from intervention devices. The Institutional Review Board (IRB) at Florida State University, approved the protocol for this trial.

Timeline & Project Flowchart

CERTIFICATION OF ASSESSORS AND INTERVENTIONISTS

All assessors and interventionists who obtain informed consent and/or administer study protocols have already completed CITI training course. In addition, undergraduate and post-bachelor's research assistants have been taught proper procedures and will be directly supervised by the study PI's or someone listed as a co-investigator of research staff in FSU IRB.

SAMPLE RECRUITMENT & RETENTION

Inclusion & Exclusion Criteria

Inclusion

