- The objective of the study is for you to **play Brain HQ for 1 hour each day, 5 days a week.**
- The hour should consist of 2 training sessions lasting 30 minutes.
- 1 week into the study, someone from our research team will contact you by phone to make sure you aren't having difficulties.
- In roughly 1 month, you will return to the lab for post testing.

122570

Brain HQ Schedule (Example 1- Weekend Breaks)

	Sun	Mon	Tue	Wed	Thu	Fri	Sat
Week 0		Baseline Test 1 (complete)	Baseline Test 2 (complete)	Laptop Training (complete)	Day 1 Brain HQ (1 hour)	Day 2 Brain HQ (1 hour)	Rest
Week 1	Rest	Day 3 Brain HQ (1 hour)	Day 4 Brain HQ (1 hour)	Day 5 Brain HQ (1 hour)	Day 6 Brain HQ (1 hour)	Day 7 Brain HQ (1 hour)	Rest
Week 2	Rest	Day 8 Brain HQ (1 hour)	Day 9 Brain HQ (1 hour)	Day 10 Brain HQ (1 hour)	Day 11 Brain HQ (1 hour)	Day 12 Brain HQ (1 hour)	Rest
Week 3	Rest	Day 13 Brain HQ (1 hour)	Day 14 Brain HQ (1 hour)	Day 15 Brain HQ (1 hour)	Day 16 Brain HQ (1 hour)	Day 17 Brain HQ (1 hour)	Rest
Week 4	Rest	Day 18 Brain HQ (1 hour)	Day 19 Brain HQ (1 hour)	Day 20 Brain HQ (1 hour)	Post Test 1 (May Differ)	Post Test 2 (May Differ)	

Note: You may take rest days on different days, as long as you play 5 days a week for 1 hour.

Brain HQ Schedule (Example 2- Random Breaks)

	Sun	Mon	Tue	Wed	Thu	Fri	Sat
Week 0		Baseline Test 1 (complete)	Baseline Test 2 (complete)	Laptop Training (complete)	Day 1 Brain HQ (1 hour)	Day 2 Brain HQ (1 hour)	Rest
Week 1	Day 3 Brain HQ (1 hour)	Day 4 Brain HQ (1 hour)	Day 5 Brain HQ (1 hour)	Rest	Day 6 Brain HQ (1 hour)	Day 7 Brain HQ (1 hour)	Day 8 Brain HQ (1 hour)
Week 2	Rest	Day 9 Brain HQ (1 hour)	Day 10 Brain HQ (1 hour)	Day 11 Brain HQ (1 hour)	Rest	Day 12 Brain HQ (1 hour)	Rest
Week 3	Day 13 Brain HQ (1 hour)	Day 14 Brain HQ (1 hour)	Rest	Rest	Day 15 Brain HQ (1 hour)	Day 16 Brain HQ (1 hour)	Day 17 Brain HQ (1 hour)
Week 4	Day 18 Brain HQ (1 hour)	Day 19 Brain HQ (1 hour)	Day 20 Brain HQ (1 hour)	Rest	Post Test 1 (May Differ)	Post Test 2 (May Differ)	

Note: You may take rest days on different days, as long as you play 5 days a week for 1 hour.

For technical support,
please call the [name]/CREATE Lab.

[contact]

(9-5 Mon-Fri)

or email

[contact]

PARTICIPANT HANDBOOK

March 02, 2017

CREATE Research Project

Florida State University

Department of Psychology

[name]

[name]

[contact]

Table of Contents

ABOUT THIS QUICK GUIDE	3
WHAT IS THE CREATE STUDY?	3
LOGGING ON TO BRAINHQ	4

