COMPLETING A TRAINING SESSION	6
DIARY AFTER TRAINING SESSION	13
SECOND TRAINING SESSION OF THE DAY	14
DESCRIPTION OF DOUBLE DECISION	15
DESCRIPTION OF FREEZE FRAME	17
DESCRIPTION OF TARGET TRACKER	19

About this Quick Guide

The BrainHQ Quick Guide is intended to provide answers to questions about using the BrainHQ software package and about the training schedule we would like you to follow. Should questions arise that are not answered here, please call: [contact].

What is the CREATE Study?

The Center for Research and Education on Aging and Technology Enhancement (CREATE) is conducting a study on cognitive training. This study seeks to measure the possible benefits of brain training games and other types of training on older adults' performance on cognitive tests and everyday tasks such as driving and finance management. The BrainHQ software features a number of games meant to exercise different abilities. These abilities include visual processing speed, alertness and visual discrimination, and the ability to divide one's attention and ignore irrelevant distractors.

[figure not shown]
Over the course of this study you will be asked complete 2 training sessions a day, for 5 days a week for a total of one month (4 weeks). Each training session should last 30 minutes, totaling 1 hour each day.

Logging on to BrainHQ

[figure not shown]
**TASK
1**

1. To load BrainHQ you will need to click on the TASK 1 icon once.

[figure not shown]
2. TASK 1 will load the website and you will be able to access the BrainHQ website as shown in Figure 1.1.

Click the Log In button at the top right of the website. It will open the login window shown in Figure 1.2.

[figure not shown]
3. Enter the email provided for you into the box labeled email.

Email: `[contact]`

Password

4. Enter the password provided for you into the box labeled password.

Email: `[contact]`

••••••••••••••

Log In

[figure not shown]
SET NEW PASSWORD

5. Click on the Log In box after you have entered the email and password.

Completing a Training session

When you log into the BrainHQ website you will be shown a summary of your training session as seen in Figure 2.1. This will provide information on what tasks you need to complete during your training session and will also show you the order of tasks you will complete.

1. This is your training schedule for each training session. Complete 2 training sessions a day, 5 days a week, for a total of one month (4

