11. All of this information is available in the “HOW-TO-Connect” video on your desktop. Let’s play a little bit of that video now.
12. (*Play first minute of HOW-TO-Connect video on participant computer if participant is unsure of ability to connect*)

13. For this training session, we will need to connect to the wireless network of Florida State University.

BEFORE CONTINUING CLICK ON THE FSU SECURE NETWORK, enter your credentials to login to the FSU network and continue.

MiFi Device Instructions: Go grab a Mifi device from [name].

1. First click on the wireless network icon in the bottom right corner of the desktop. This will pull up a list of wireless networks. (*show where to click to pull up network list.*)
2. We will use the network **CREATE_#X** to train you on how to login to the Mifi device.
3. Click **CREATE_#X** from the list of wireless networks.
4. Click the connect button.
5. In the password prompt enter the password **CREATE2017**.
6. Click the OK button.

Introduction to Brain HQ

SPEAKING: Now I am going to give you a demonstration of how to access the Brain HQ software and the features of the software. Please feel free to ask any questions at any time during the demonstration. Please also let me know any time you would like to take a break.

Open Task 1

DEMONSTRATE: Now let's access the task, Brain HQ, and start learning it. First, you will need to:

1. Click once (do not double click) on the "Task 1" icon at the top left of your desktop.

2. This will bring you to the Brain HQ training homepage.
3. You should have your window in full screen while you complete the course.
4. Click on the maximize button at the top right corner of the browser.

Logging In

SPEAKING: You have been preassigned a login and password for this course. Your login information allows you to access and complete the course, and monitor how much of the training you have completed. Let's login to the course now and get started. (*Pause between instructions and wait for participant to attempt each step on their own. Only help if participant needs it.*)

1. First click on the log in button at the top right of the Brain HQ website.
2. This is the login window. Here you will enter the email address and password that we setup when we purchased the Brain HQ account for you.
3. The email address and password is located on the laptop, right here.
4. Now enter that email and password into the website to login.
5. Then click the "Log In" button.

Today's Schedule Page

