DEMONSTRATE: For the rest of today’s lab training session, we want you to resume the AARP driver’s safety course and complete **Unit 1**. This time you will try to start the AARP course based on what you just learned. I will be here to answer any questions you may have and help guide you through your training. But we also want you to attempt to use the take-home manual as practice for the time when you are alone at home and might have a question that the manual could answer. Let’s start the course when you’re ready.

(Watch if the participant can figure out how to get back to AARP and start Unit 1. Remind participants of that all the necessary information needed is described in the take-home manual and encourage them to use the manual from this point if they have questions, so that they can

also learn how to find information from it. If you have any questions, you can also refer to the take-home manual to guide participants.

(Once they finish the unit 1, ask them to stop the course and fill out the diary)

End of Lab Training Session

AFTER COMPLETING AARP UNIT 1 & Diary: Do you have any questions or anything that needs clarification before we end our training?

(Interventionist should answer any questions. Also please emphasize that we want them to complete each course twice and follow the training schedule attached in the manual. Especially, tell them they don't go to the last unit of each course – unit 6 for the AARP driver's course and unit 8 for Finances and Fraud course if it is "the first time". Please show them the training schedule!!!)

Control training (Crosswords, Sudoku, Word Search)

Call Scripts

One week call - CHECK IN

Hi, this is [your name] from the CREATE lab at FSU. Is _____ there? So, it's been a week since you were given a the laptop as part of your participation in the CE study and I'm just calling to check in and make sure you're not having any problems with [the condition] or with the laptop in general.

Setup appointment - POST

Hi, this is [your name] from the CREATE lab at FSU. Is _____ there? I was just calling to remind you of your two post testing days are [post testing days], and we ask that you bring in the

laptop and all other materials with you when you come in for those days. If you have any questions please call [contact]. Thank you.

Setup appointment - FOLLOW UP

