#### **EFFICACY ANALYSES FOR PRIMARY & SECONDARY OUTCOME VARIABLES**

Analyses Immediately following training

1. We plan 4 arms (Brain HQ, Rise of Nations, Driving and Fraud Avoidance Training, Puzzle Solving) x 2 times of measurement (baseline, post-training) ANOVAs (or ANCOVAs) for the following primary variables: fraud detection accuracy score, Driving Hazard Perception Test (safety and accuracy of navigation), Self-reported IADL task, Speed of Processing.

2. We plan 4 arms (Brain HQ, Rise of Nations, Driving and Fraud Avoidance Training, Puzzle Solving) x 2 times of measurement (baseline, post-training) ANOVAs (or ANCOVAs) for the following secondary variables: Technology Proficiency (CPQ & MDPQ average z-scored variables), Numeracy (accuracy on Berlin Numeracy Test), Reasoning Ability (average z-scored variables for Letter Sets & Ravens), Memory Ability (Average z-scored variables for Hopkins Verbal Learning Test and Rey Auditory Verbal Learning Test), Miami IADL task.

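### The post-test reminder has participants bring their laptop and training materials to the outcome visits, and no visible text keeps the tester from learning the arm

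*Protocol*

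**What the plan says.** Under Overall design, the Protocol says that once assigned to a condition, "they received a laptop with specialized software for their condition". Participants train at home for four weeks and then "return for two scheduled days of post-training assessments". The same section counts among the standardised procedures "intervention administration (including manuals sent home with participants), and data transfer from intervention devices", so manuals are part of what participants hold at home.

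The POST reminder asks them to bring the "laptop and all other materials with you when you come in for those days". The 12-month reminder (Setup appointment - FOLLOW UP) makes no such request.

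The BrainHQ items shown in full identify the arm. The schedule sheet is headed "Brain HQ Schedule (Example 1- Weekend Breaks", and the handbook opens with "The BrainHQ Quick Guide is intended to provide answers to questions about using the BrainHQ software package". The BrainHQ training script adds a possible further cue: "The email address and password is located on the laptop, right here". The IADL script says the same for the driving course account.

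The Protocol's section on certification of staff names assessors and interventionists together and does not separate the roles. The one-week check-in script has the caller name the participant's condition.

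**The concern.** The Protocol's introduction treats expectation effects as a serious threat to training studies. An active control and measurement of expectation are among its stated design features. Those address what participants expect. A tester who knows the arm adds a second route, through pacing, encouragement and, where answers are marked by hand, scoring.

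The route opens at the visit that supplies the immediate post-training scores. Those scores enter the SAP's arm-by-time analyses and the gain-per-hour comparison. If tester knowledge follows the arm, its effect cannot be told apart from the arm effect in those models, and neither document plans to record what testers knew or guessed.

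**Working it through.** The documents give no figure that bears on this point, so there is nothing to recompute. The check sets the texts side by side.

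1. **Do the materials arrive at an outcome visit?** Yes. The POST script attaches the request to the post-testing days, and Overall design defines these as the post-training assessments.

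2. **Do the materials reveal the arm?**
   - BrainHQ: yes. The schedule sheet names the product in its title and the handbook names it in its contents and text. The visible handbook heading itself is neutral and gives only the project name.
   - Rise of Nations, IADL and control: not known. Their take-home manuals appear only as headings. The IADL script does refer to a manual containing a course schedule, and the Rise of Nations script refers to a manual.
   - Laptop: not necessarily. The desktop icons carry neutral labels (Task 1, Task 2). The BrainHQ account email is removed from the text, so whether it names the arm cannot be read. The fraud course password is the same generic one used for the wireless network.

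3. **Does it matter if only some arms can be recognised?** Yes. Recognising BrainHQ alone would let a tester treat that arm differently from the other three, and every comparison with BrainHQ would be exposed.

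4. **Would the baseline score cancel it?** No. Randomisation follows the baseline assessments, so a baseline tester cannot know the arm. Any influence would act on the post-training score only and would stay in the change score.

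5. **Is there a safeguard?** None in the visible text. Nothing says who receives the equipment, when, or out of whose sight. Nothing asks participants to keep their programme to themselves. The headings for the battery and for randomisation procedures have no readable text beneath them, so a rule there cannot be ruled out.

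6. **Are there other routes to the same knowledge?** Yes. Staff train each participant in person on the assigned task, and the one-week caller names the condition. If the same person later tests, hiding the bag masks nobody.

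7. **Which outcomes could move?** The immediate primary outcomes cover fraud detection, driving hazard perception, self-reported everyday function and processing speed. These are accuracy, speed or self-report measures, which leave little room for subjective marking. The clearest candidates are in the SAP's secondary list: "Memory Ability (Average z-scored variables for Hopkins Verbal Learning Test and Rey Auditory Verbal Learning Test), Miami IADL task". The memory composite is the stronger example, on the assumption that a staff member presents the word lists and records recall.

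**The case against.** The strongest reply is that exposure is not shown. No text says that the tester receives the equipment, or sees it before testing. A closed laptop and a neutral icon reveal nothing, and only one arm's manual can be read. That stands. A reader might infer that every post-training visit in all four arms is unmasked; the documents support only that participants are told to bring the items.

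Second, assessor masking is never promised, so the script contradicts nothing. That also stands. The point is an unprotected risk, not an inconsistency.

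Third, the bag is a minor route if the trainer or caller may also be the tester. This is right, and it shapes the remedy: hiding the materials is useful only together with separate staff. It is no reason to leave the script as it is.

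Fourth, the outcome link is thin, because the best example is secondary and rests on an assumption about administration. That is fair. A reader might infer a bias in the primary outcomes, but the documents show no specific mechanism for them.

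Finally, holding the laptop back until the second test day would leave working training software with participants between the two sessions. That is a real cost of late return, and hand-in on arrival avoids it.

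**Conclusion.** The point holds in a limited form. Followed as written, the POST script brings materials that identify the arm, certainly for BrainHQ, to the visits where immediate outcomes are measured. No visible text prevents the tester from learning the arm before the post-test.

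The size of any bias cannot be derived: the documents give no standard deviation, expected effect or sample size, and nothing on how far a tester's knowledge moves a score. Any figure would be a guess, so none is offered. The risk is most plausible for staff-administered measures, on the stated assumption about the verbal learning tests. Through this script it is confined to the immediate post-test, since the 12-month script does not ask for materials.

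The documents do not support saying that testers saw the items, that all arms were revealed, or that the primary results are biased. The change is worth making because it closes an avoidable route at small cost.

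**What to change.** Change the POST script to say, in substance:

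> Please bring the laptop and all your materials in the closed bag. When you arrive, give the bag to the lab member who meets you, who will not be testing you. Please do not tell the person testing you which programme you used.

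If no second person is free, the bag should stay closed until the last measure is finished. Issue the bag with the laptop; the visible documents do not mention one.

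Pair this with a scheduling rule: the post-test tester is an existing staff member who neither trained nor telephoned that participant. Add a sentence to the Protocol stating whether testers are masked to arm, and have testers record their guess of the arm after the last measure. If post-testing is already complete, report who tested and whether they knew the arm.

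The cost is a few script sentences, a bag for each laptop and some scheduling effort. No outcome, sample size or analysis changes. Some participants will still disclose, and the recorded guess would help show how often.

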**ANALYSIS PLAN for ICE-ACT 7/3/2017 as registered on OSF site:**

Type: Statistical Analysis Plan

URL: <https://osf.io/kq8yz/register/565fb3678c5e4a66b5582f67>

Identifier: <https://osf.io/dp8n5/>

Open Science Foundation registration of Data Analysis Plan

#### **EVALUATION OF RANDOM ASSIGNMENT**

1. We plan to compare the 4 arms at baseline on the variables of age, education level, and gender and on the primary and secondary outcome variables (MANOVA across variables) to assess if random assignment resulted in equivalence across groups. If it did not, then we plan to use ANCOVAs in the next stage rather than ANOVAs, controlling for baseline differences on these variables.

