This randomized trial was designed to compare the effectiveness of broad and directed (narrow) technology-based training on basic perceptual and cognitive abilities in older adults and on the performance of simulated tasks of daily living. Participants were randomly assigned to four training conditions: (1) a brain game; (2) a video game; (3) IADL training for both fraud avoidance and driving; or (4) an active control condition, involving puzzle solving. This trial seeks to provide guidance not just about what works, but also what works best for a given investment (i.e., time, money) in older adults. The current trial was specifically designed to

address the several methodological limitations mentioned above, including: (1) the development of direct measures of IADL performance, targeting areas related to risks for catastrophic failure (e.g., crashes in driving, losing financial resources to fraud); (2) the use of alternate forms to provide more precise estimates of treatment effects (for both cognitive and IADL measures); (3) inclusion of an active control condition; and (4) measurement of expectation effects (as recommended in [43]). In this paper, we provide a primer to the design of this trial and describe the baseline characteristics of our sample.

Overall design

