#### Analyses following one-year follow-up

3. We plan 4 arms (Brain HQ, Rise of Nations, Driving and Fraud Avoidance Training, Puzzle Solving) x 2 times of measurement (baseline, 1-year follow-up) ANOVAs (or ANCOVAs) for the following primary variables: fraud detection accuracy score, Driving Hazard Perception Test (safety and accuracy of navigation), Self-reported IADL task, Speed of Processing, Knowledge about Driving (accuracy), Knowledge about Finances and Fraud (accuracy).

4. We plan 4 arms (Brain HQ, Rise of Nations, Driving and Fraud Avoidance Training, Puzzle Solving) x 2 times of measurement (baseline, 1-year follow-up) ANOVAs (or ANCOVAs) for the following secondary variables: Technology Proficiency (CPQ & MDPQ average z-scored variables), Numeracy (accuracy on Berlin Numeracy Test), Reasoning Ability (average z-scored variables for Letter Sets & Ravens), Memory Ability (Average z-scored variables for Hopkins Verbal Learning and Rey Auditory Verbal Learning Test), Miami IADL task.

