### COMPARATIVE EFFECTIVENESS ANALYSES

#### Analyses immediately following training

1. Immediate gain scores (post-training - baseline)/hours of reported training, for above primary and secondary variables will be compared across Arms.

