#### Analyses following one-year follow-up

2. Long-term gain scores (1-year follow-up - baseline)/hours of reported training, for above primary and secondary variables will be compared across Arms.

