### EXPLORATORY ANALYSES OF INDIVIDUAL DIFFERENCE PREDICTORS OF GAIN

We will use multiple regression analyses to predict the above post-test and 1 year gain scores on primary and secondary variables from age, education, gender, occupation, expectation for improvement, and study arm.

---

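### Baseline adjustment depends on a check for chance imbalance; the default 4 x 2 ANOVA fixes the baseline slope at 1 and in large samples is at best as precise as ANCOVA

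*SAP*

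**What the plan says.** The SAP section on evaluation of random assignment compares the arms on age, education, gender and all primary and secondary outcomes, and labels this a MANOVA. It gives no alpha and no threshold for equivalence. On failure of the check it states: "If it did not, then we plan to use ANCOVAs in the next stage rather than ANOVAs, controlling for baseline differences on these variables".

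The efficacy sections carry this choice into every primary and secondary outcome. At post-training the model is 4 arms "x 2 times of measurement (baseline, post-training) ANOVAs (or ANCOVAs"), and at one year 4 arms "x 2 times of measurement (baseline, 1-year follow-up) ANOVAs (or ANCOVAs"). Baseline is therefore a level of the time factor in the default model, not a covariate.

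No other section adjusts unconditionally for an outcome's own baseline:

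- The comparative effectiveness analyses use raw gain divided by reported hours, "for above primary and secondary variables will be compared across Arms". The one-year version is "Long-term gain scores (1-year follow-up - baseline)/hours of reported training".
- The exploratory regressions predict gain "from age, education, gender, occupation, expectation for improvement, and study arm". Baseline score is not in that list.

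**The concern.** The SAP does not name the arm-by-time term, but that is the term that tests differential change. With two times it is the same test as a one-way ANOVA on follow-up minus baseline. Baseline is used, but with its coefficient set to 1. When the true slope is not 1, the change score stays correlated with baseline. That adds avoidable variance and leaves the estimate tied to any chance baseline difference.

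The check does not address this. The benefit of adjustment depends on how well baseline predicts the outcome, whereas the check looks at observed imbalance, which in a randomised trial arises by chance. At stake are precision on all primary and secondary outcomes, and conditional bias in the trials where an outcome happens to be unbalanced at baseline.

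The triggered analysis is also not fully specified. The covariates could be all the listed variables or only those found to differ. Nor does the SAP say how an outcome's baseline can be both a time level and a covariate. Entered only as a main effect, without a time interaction, it would leave the arm-by-time test unchanged.

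**Working it through.** The plan states no power or sample size figure on this point, so there is none to reproduce.

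**Inputs.** From the documents: four randomised arms, two times per analysis, and 12 to 15 variables in the baseline check (3 demographic, 4 to 7 primary depending on how they are counted, 5 secondary). Assumed: correlation rho between baseline and follow-up, ratio k of follow-up SD to baseline SD, n per arm, 5% two-sided alpha, and one arm better than the other three by 0.4 baseline SD.

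**Variance.** With baseline SD 1 and follow-up SD k, per participant:

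- Var(change) = 1 + k² − 2·rho·k
- Var(ANCOVA) = k²(1 − rho²)
- Difference = (1 − rho·k)², which is never negative and is zero only when the slope rho·k equals 1

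Example: k = 1 and rho = 0.5 give 1.00 against 0.75, an excess of 33%.

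| Excess variance of change score | rho 0.5 | 0.6 | 0.7 | 0.8 | 0.9 |
|---|---|---|---|---|---|
| k = 1 | 33% | 25% | 18% | 11% | 5% |
| k = 1.2 | 15% | 9% | 3% | 0.3% | 2% |
| k = 0.8 | 75% | 66% | 59% | 56% | 64% |

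**Finite samples.** Estimating the slope multiplies the ANCOVA variance by 1 + 1/(N − 6), with N = 4n. The most the change score can gain (slope exactly 1) is therefore 1/154 = 0.65%, 1/234 = 0.43% and 1/314 = 0.32% at 40, 60 and 80 per arm.

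**Power.** This uses a noncentral F with 3 numerator df and noncentrality n × 0.12/V, where 0.12 = 0.4² × 3/4. For ANCOVA, V includes the factor above. At 60 per arm, k = 1 and rho = 0.5, the noncentrality is 7.2/1 = 7.2 for change and 7.2/(0.75 × 1.0043) = 9.56 for ANCOVA.

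| Power at 60 per arm, change v ANCOVA | rho 0.5 | 0.6 | 0.7 | 0.8 | 0.9 |
|---|---|---|---|---|---|
| k = 1 | 60 v 73% | 70 v 81% | 83 v 89% | 96 v 97% | 100 v 100% |
| k = 1.2 | 50 v 56% | 60 v 63% | 73 v 74% | 89 v 89% | 99 v 99% |
| k = 0.8 | 68 v 91% | 78 v 95% | 89 v 98% | 97 v 100% | 100 v 100% |

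With k = 1, power at 40 per arm is 42 v 53% (rho 0.5) and 64 v 72% (rho 0.7). At 80 per arm it is 74 v 86% and 93 v 96%.

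**What the check recovers.** These figures are from simulation at 60 per arm, with k = 1 and 14 baseline variables with mutual correlation 0.3. A triggered ANCOVA is taken to use the outcome's own baseline.

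| Power | Change | One-MANOVA check | Separate 5% tests | Always ANCOVA |
|---|---|---|---|---|
| rho 0.5 | 59% | 60% | 65% | 73% |
| rho 0.7 | 84% | 84% | 87% | 89% |

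One MANOVA at 5% opens in about 5% of properly randomised trials. Given an imbalance of at least 0.3 SD between two arms in one outcome's baseline, it opens in 9 to 10% at 60 per arm. With 12 to 15 separate tests the figures are 40 to 54% overall and 57 to 63% given that imbalance.

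**Chance imbalance.** The probability that a given pair of arms differs by at least 0.3 SD is 2·P(Z > 0.3/√(2/n)) = 18%, 10% and 6% at 40, 60 and 80 per arm. With k = 1 the change-score contrast shifts by imbalance × (1 − rho). The shift is at least 0.15, 0.09 and 0.03 SD at rho 0.5, 0.7 and 0.9, and at 60 per arm it averages 0.19, 0.11 and 0.04 SD.

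**Type I error.** In the four-strategy simulation, null rejection was 4.2 to 5.4% for every strategy. In a separate simulation that checked only the outcome's own baseline, the default ANOVA rejected a true null in about 7 to 9% of runs when the baseline p-value was between 0.05 and 0.20, so that the check passed.

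**The case against.** The strongest reply is that the default analysis is sound. It uses baseline, is unbiased over randomisation and holds its error rate. The size of the loss in this trial is unknown, because the documents give none of the quantities that determine it. If the follow-up SD is 1.2 times the baseline SD, the power gap at 60 per arm is at most about 6 points and vanishes by rho 0.8. With equal SDs it is under 2 points at rho 0.8. All of this stands. It limits the point to precision and conditional bias, and it means that 60% against 73% is one illustration and not an estimate for this trial. A follow-up SD of 0.8 times baseline widens the gap instead.

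A second objection is that the 65% and 87% shown for separate tests assume that the outcome's own baseline enters as soon as any variable differs. That is correct, and the SAP does not settle it. If own baseline enters only when it differs itself, simulated power is about 60%, against 59% for change and 75% for always-ANCOVA at rho 0.5. A further run at rho 0.7 gave 83.6% against 83.4% for change. The check then recovers almost nothing, so this objection makes the concern stronger.

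A third objection is that the plan is a dated registration, headed "ANALYSIS PLAN for ICE-ACT 7/3/2017 as registered on OSF site", and should not be rewritten freely. That is fair, and it governs how the change is made.

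**Conclusion.** The concern holds. ANCOVA is conditional on a baseline check that has no stated threshold. The default arm-by-time test fixes the baseline slope at 1, and no other analysis supplies unconditional adjustment. The algebra needs no assumption about this trial: in large samples the default is at best as precise as ANCOVA, and in finite samples its advantage can be no more than 0.65% of variance at 40 per arm and less in larger arms. The size of the loss does rest on assumed values. Over rho 0.5 to 0.9 and SD ratios 0.8 to 1.2, the excess variance runs from 0.3% to 75%, and it is 5% to 33% with equal SDs. This should be fixed. It is not an error in validity.

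**What to change.** Remove the conditional rule. For every primary and secondary outcome, at post-training and at one year, prespecify ANCOVA of the follow-up score on arm with that outcome's own baseline score as covariate. Do not also carry baseline as a level of a time factor. Keep the baseline comparison as description only.

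Make the change by a dated amendment to the registered plan that states whether outcome data had been seen. The Protocol reports randomisation in the past tense and sets out to "describe the baseline characteristics of our sample", so the question is a real one. If outcomes had not been seen, the ANCOVA replaces the registered analysis. If they had, report the ANCOVA beside the registered analysis and label it as added later.

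The cost is one degree of freedom per analysis and the amendment. No new data are needed, because baseline scores are already collected. The gain-per-hour comparisons are also unadjusted, but they raise a separate question through the division by reported hours, and this change does not cover them.
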